#### **4.5.1. Safety Variables**

Safety, reactogenicity, and tolerability will be assessed by:

1. Frequency and Severity of Solicited Adverse Events – reactogenicity events occurring from vaccination through 7 days after each dose of vaccine is administered:
  - a) Local solicited events include: irritation of the oral cavity or tongue, diarrhea, nausea, vomiting, and abdominal discomfort for Oral Cohorts; irritation of the oral cavity or tongue, facial nerve disturbance, diarrhea, nausea, vomiting, or abdominal discomfort for Sublingual Cohorts; and injection site pain, redness, swelling, bruising, itching, hypo/hyper pigmentation and induration, vesicles or hardened mass for Intradermal Cohorts.
  - b) Systemic solicited events include: fever, feverishness, fatigue, malaise, myalgia, or headache for Oral and Sublingual Cohorts; and fever, feverishness, fatigue, malaise, myalgia, headache, diarrhea, nausea, vomiting, or abdominal discomfort for Intradermal Cohorts.
2. Frequency of participant withdrawals from first vaccination through the end of follow-up (Day 209 for Oral and Sublingual Cohorts, Day 223 for Intradermal Cohorts)
3. Frequency of discontinuation of study vaccination during the study

4. Frequency and severity of unsolicited vaccine-related non-serious adverse events (AE), including laboratory AE, from first vaccination through 28 days after the last dose of vaccine is administered (Day 57 for Oral and Sublingual Cohorts, Day 71 for Intradermal Cohorts)
5. Frequency of vaccine-related SAEs from the first vaccination through the end of follow-up (Day 209 for Oral and Sublingual Cohorts, Day 223 for Intradermal Cohorts)

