#### 6.3.1. Safety Population

The Safety Analysis population will include all eligible participants who received at least one dose of study product.

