## 9.3. Adverse Events

When calculating the incidence of adverse events (i.e., on a per participant basis), each participant will only be counted once and any repetitions of adverse events within a participant will be ignored; the denominator will be the total population size. All adverse events reported will be included in the summaries and analyses.

An overall summary of adverse events by treatment group is presented in [Table 91](#) and [Table 92](#). Unsolicited adverse events occurring in more than 5% of participants in any treatment group are presented in [Table 93](#) and [Table 94](#).

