**15. SUMMARY OF CHANGES IN THE CONDUCT OF THE STUDY OR PLANNED ANALYSES****Changes to Study Conduct**

- At the request of the local (icddr,b) DSMB, collection of serum bilirubin at screening and Visit 6 and collection of ALT and creatinine at Visit 6 were added to the safety labs. These results were not obtained for Cohorts A through C which were enrolled prior to the request.
- Due to a country-wide lockdown instituted in Bangladesh to combat the COVID-19 pandemic all Cohort E participants did not receive a third dose of study product. Cohort D participant Visits 8 and 9 and Cohort E participant Visits 6 through 9 were not conducted and no further cohorts were enrolled due to the pandemic.

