**Table 90: Correlation of ASC IgG Count vs ALS IgG Titers GMFR by Time Point and Treatment Group, Per Protocol Population**

## 14.3 Safety Data

### 14.3.1 Displays of Adverse Events

**Table 91: Overall Summary of Adverse Events - Oral & Sublingual Cohorts**

	Cohort A: Oral 5 µg dmLT (N=X)		Cohort B: Oral 25 µg dmLT (N=X)		All Oral Cohorts: Placebo (N=X)		All Oral Route Subjects (N=X)		Cohort C: Sublingual 5 µg dmLT (N=X)		Cohort D: Sublingual 25 µg dmLT (N=X)		All Sublingual Cohorts: Placebo (N=X)		All Sublingual Route Subjects (N=X)	
Subjects a with	n	%	n	%	n	%	n	%	n	%	n	%	n	%	n	%
At least one local solicited adverse event	x	x	x	x	x	x	x	x	x	x	x	x	x	x	x	x
At least one systemic solicited adverse event	x	x	x	x	x	x	x	x	x	x	x	x	x	x	x	x
At least one unsolicited adverse event	x	x	x	x	x	x	x	x	x	x	x	x	x	x	x	x
At least one related unsolicited adverse event, through 28 days after the last dose	x	x	x	x	x	x	x	x	x	x	x	x	x	x	x	x
Mild (Grade 1)	x	x	x	x	x	x	x	x	x	x	x	x	x	x	x	x
Moderate (Grade 2)	x	x	x	x	x	x	x	x	x	x	x	x	x	x	x	x
Severe (Grade 3)	x	x	x	x	x	x	x	x	x	x	x	x	x	x	x	x
Not yet assessed																
At least one related unsolicited adverse event, from first vaccination through 6 months after the last dose	x	x	x	x	x	x	x	x	x	x	x	x	x	x	x	x
Mild (Grade 1)	x	x	x	x	x	x	x	x	x	x	x	x	x	x	x	x
Moderate (Grade 2)	x	x	x	x	x	x	x	x	x	x	x	x	x	x	x	x
Severe (Grade 3)	x	x	x	x	x	x	x	x	x	x	x	x	x	x	x	x
Not yet assessed																

	Cohort A: Oral 5 µg dmLT (N=X)		Cohort B: Oral 25 µg dmLT (N=X)		All Oral Cohorts: Placebo (N=X)		All Oral Route Subjects (N=X)		Cohort C: Sublingual 5 µg dmLT (N=X)		Cohort D: Sublingual 25 µg dmLT (N=X)		All Sublingual Cohorts: Placebo (N=X)		All Sublingual Route Subjects (N=X)	
Subjects a with	n	%	n	%	n	%	n	%	n	%	n	%	n	%	n	%
At least one severe (Grade 3) unsolicited adverse event	x	x	x	x	x	x	x	x	x	x	x	x	x	x	x	x
Related	x	x	x	x	x	x	x	x	x	x	x	x	x	x	x	x
Unrelated	x	x	x	x	x	x	x	x	x	x	x	x	x	x	x	x
At least one serious adverse event b	x	x	x	x	x	x	x	x	x	x	x	x	x	x	x	x
At least one related, serious adverse event	x	x	x	x	x	x	x	x	x	x	x	x	x	x	x	x
At least one adverse event leading to early termination c	x	x	x	x	x	x	x	x	x	x	x	x	x	x	x	x
Study withdrawal for any reason	x	x	x	x	x	x	x	x	x	x	x	x	x	x	x	x
Discontinuation of study vaccination for any reason	x	x	x	x	x	x	x	x	x	x	x	x	x	x	x	x

N = Number of subjects in the Safety Population

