**Table 92: Overall Summary of Adverse Events - Intradermal & Pooled Cohorts**

*[Implementation note: Treatment groups are Cohort E: Intradermal 0.3 µg dmLT (N=X), Cohort E: Intradermal Placebo (N=X), and All Intradermal Route Subjects (N=X). All Subjects (N=X) will be added at the end.]*

**Table 93: Adverse Events Occurring in 5% of Subjects in Any Treatment Group by MedDRA System Organ Class and Preferred Term, and Treatment Group – Oral & Sublingual Cohorts**

MedDRA Preferred Term	MedDRA System Organ Class	Cohort A: Oral 5 µg dmLT (N=X)			Cohort B: Oral 25 µg dmLT (N=X)			All Oral Cohorts: Placebo (N=X)			All Oral Route Subjects (N=X)			Cohort C: Sublingual 5 µg dmLT (N=X)			Cohort D: Sublingual 25 µg dmLT (N=X)			All Sublingual Cohorts: Placebo (N=X)			All Sublingual Route Subjects (N=X)						
		n	%	Events	n	%	Events	n	%	Events	n	%	Events	n	%	Events	n	%	Events	n	%	Events	n	%	Events	n	%	Events	
Serious Adverse Events																													
All	All	x	x	x	x	x	x	x	x	x	x	x	x	x	x	x	x	x	x	x	x	x	x	x	x	x	x		
PT1	SOC1	x	x	x	x	x	x	x	x	x	x	x	x	x	x	x	x	x	x	x	x	x	x	x	x	x	x		
Etc.	Etc.																												
Other (Non-serious) Adverse Events																													
All	All	x	x	x	x	x	x	x	x	x	x	x	x	x	x	x	x	x	x	x	x	x	x	x	x	x	x		
PT1	SOC1	x	x	x	x	x	x	x	x	x	x	x	x	x	x	x	x	x	x	x	x	x	x	x	x	x	x		
Etc.	Etc.																												

N = number of subjects in the Safety Population (number of subjects at risk).

n= number of subjects reporting event.

Events= total frequency of events reported.

Tables with similar format:

**Table 94: Adverse Events Occurring in 5% of Subjects in Any Treatment Group by MedDRA System Organ Class and Preferred Term, and Treatment Group – Intradermal & Pooled Cohorts**

*[Implementation note: Treatment groups are Cohort E: Intradermal 0.3 µg dmLT (N=X), Cohort E: Intradermal Placebo (N=X), and All Intradermal Route Subjects (N=X). All Subjects (N=X) will be added at the end.]*

**Table 95: Serious Adverse Events by MedDRA System Organ Class and Preferred Term, and Treatment Group – Oral & Sublingual Cohorts****Table 96: Serious Adverse Events by MedDRA System Organ Class and Preferred Term, and Treatment Group – Intradermal & Pooled Cohorts**

*[Implementation note: Treatment groups are Cohort E: Intradermal 0.3 µg dmLT (N=X), Cohort E: Intradermal Placebo (N=X), and All Intradermal Route Subjects (N=X). All Subjects (N=X) will be added at the end.]*

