**14.3.1.1      Solicited Adverse Events****Table 97:      Number and Percentage of Subjects Experiencing Solicited Events with 95% Confidence Intervals by Symptom, Dose, and Treatment Group – Cohort A: Oral 5 µg dmLT**

Symptom	Post Dose 1 (N=X)			Post Dose 2 (N=X)			Post Dose 3 (N=X)			Post Any Dose (N=X)		
	n	%	95% CI	n	%	95% CI	n	%	95% CI	n	%	95% CI
Any Symptom	x	xx	x.x, x.x	x	xx	x.x, x.x	x	xx	x.x, x.x	x	xx	x.x, x.x
Any Systemic Symptom												
Fever												
Feverishness												
Fatigue												
Malaise												
Myalgia												
Headache												
Any Local Symptom												
Irritation of the Oral Cavity or Tongue												
Diarrhea												
Nausea												
Vomiting												
Abdominal Discomfort												

Note: N=Number of subjects in the Safety Population

Tables with similar format:

**Table 98:      Number and Percentage of Subjects Experiencing Solicited Events with 95% Confidence Intervals by Symptom, Dose, and Treatment Group – Cohort B: Oral 25 µg dmLT****Table 99:      Number and Percentage of Subjects Experiencing Solicited Events with 95% Confidence Intervals by Symptom, Dose, and Treatment Group – All Oral Cohorts: Placebo**

**Table 100: Number and Percentage of Subjects Experiencing Solicited Events with 95% Confidence Intervals by Symptom, Dose, and Treatment Group – Cohort C: Sublingual 5 µg dmLT**

*[Implementation note: Systemic symptoms presented will be fever, feverishness, fatigue, malaise, myalgia, or headache. Local symptoms presented will be irritation of the oral cavity or tongue, facial nerve disturbance, diarrhea, nausea, vomiting, or abdominal discomfort.]*

**Table 101: Number and Percentage of Subjects Experiencing Solicited Events with 95% Confidence Intervals by Symptom, Dose, and Treatment Group – Cohort D: Sublingual 25 µg dmLT**

*[Implementation note: Systemic symptoms presented will be fever, feverishness, fatigue, malaise, myalgia, or headache. Local symptoms presented will be irritation of the oral cavity or tongue, facial nerve disturbance, diarrhea, nausea, vomiting, or abdominal discomfort.]*

**Table 102: Number and Percentage of Subjects Experiencing Solicited Events with 95% Confidence Intervals by Symptom, Dose, and Treatment Group – All Sublingual Cohorts: Placebo**

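### AE and SAE percentages divide by the full Safety Population although Cohorts D and E missed the 6-month visit and Cohort E's 28-day window was not completed

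*SAP*

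**What the plan says.** **Denominator.** SAP 9.3 sets the per-participant incidence rule: "the denominator will be the total population size". SAP 6.3.1 defines the population without any follow-up condition: "The Safety Analysis population will include all eligible participants who received at least one dose of study product". Table 91 carries the footnote "N = Number of subjects in the Safety Population", and Table 92 follows its format. Table 93 also uses the Safety Population and describes that number as the participants at risk. SAP 6.5 rules out imputation.

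**Windows.** SAP 4.5.1 lists "Frequency of vaccine-related SAEs from the first vaccination through the end of follow-up", ending on Day 209 (oral, sublingual) or Day 223 (intradermal). Unsolicited events run to 28 days after the last dose, given as Day 57 or Day 71. Table 91 has a further row: "At least one related unsolicited adverse event, from first vaccination through 6 months after the last dose", broken down by grade.

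**What happened.** SAP 15 reports that "Cohort D participant Visits 8 and 9 and Cohort E participant Visits 6 through 9 were not conducted" and that Cohort E received no third dose. SAP 4.4.5 puts Cohort E's two doses on Days 1 and 22.

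**Solicited events.** Table 97 has a Post Dose 3 column and the note "Note: N=Number of subjects in the Safety Population". Tables 103 and 104 reuse this format for Cohort E, and their implementation notes change only the symptom lists.

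**The concern.** With a count over a fixed N and no imputation, a participant whose window was cut short contributes a full unit to the denominator and can contribute events only from the observed part. The rest of the window is treated as event-free. This affects a secondary endpoint (vaccine-related SAEs to 6 months) in Cohorts D and E, and a primary endpoint (vaccine-related unsolicited AEs to 28 days after the last dose) in Cohort E. These are the highest sublingual dose actually given and the only intradermal cohort.

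The SAP was written after the study stopped, and other shells already allow for the gap. The 85- and 180-day vital-sign rows omit D and E. The 28-day laboratory rows omit E, and the laboratory grading tables have a Missing column. The AE and SAE tables have no equivalent.

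**Working it through.** **1. Reproduce the plan's own bound.** SAP section 5 gives exact upper 95% bounds for zero events. The two-sided Clopper-Pearson upper limit for 0/n is 1 − 0.025^(1/n).

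| n | Formula | SAP |
|---|---|---|
| 10 | 30.8% | 30.8% |
| 20 | 16.8% | 16.8% |
| 40 | 8.8% | 8.8% |
| 60 | 6.0% | 6.0% |

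The same formula is used below.

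**2. Who lacks which window.** Visit days are from SAP Tables 2 and 3.
- Cohort D: Visits 8 and 9 (Days 114 and 209) were missed. Visit 7 (Day 57) is not listed as missed, so the 28-day window is complete and the 6-month window is not.
- Cohort E: Visits 6 to 9 (Days 50, 71, 128 and 223) were missed. The last dose was on Day 22, and 22 + 28 = Day 50, so no scheduled visit took place at or after the end of the 28 days. The last vital signs in SAP 9.7 are from Day 29 (29 − 22 = 7 days after dose 2). Visit 5 (Day 43, 43 − 22 = 21 days) is not listed as missed, so contact then cannot be excluded. Either way the 28 days are incomplete.
- Share of scheduled follow-up covered: Cohort D (57 − 1)/(209 − 1) = 56/208 = 27%. Cohort E 28/222 = 13%, or 42/222 = 19% if seen on Day 43.

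**3. Numbers.** Assume the planned 12 dmLT + 3 placebo = 15 per cohort (SAP 4.4.3). Cohorts A–E then have 75 participants and 60 vaccinees. D and E together have 30 participants and 24 vaccinees, 40% in each case. Those with the scheduled 6-month visit number at most 45 and 36.

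**4. Effect on a 6-month percentage.** If D and E record no events, the printed value is 45/75 = 0.60 of the value in Cohorts A–C. One event would read 1/75 = 1.3% instead of 1/45 = 2.2%. In the all-sublingual column the factor is 15/30 = 0.50.

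**5. Zero-event upper limits, if computed.**

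| Group and window | Plan's N | Limit | N with window complete | Limit |
|---|---|---|---|---|
| All participants, 6 months | 75 | 4.8% | 45 | 7.9% |
| Vaccinees, 6 months | 60 | 6.0% | 36 | 9.7% |
| All participants, 28 days | 75 | 4.8% | 60 | 6.0% |

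**6. Sensitivity to cohort size.** Actual counts are not given. SAP section 5 cites 40 three-dose vaccinees in A–D, not 4 × 12 = 48. At 10 vaccinees per cohort the 6-month limits would be 7.1% (0/50) against 11.6% (0/30). The factor of 0.60 holds for any equal cohort size.

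**7. Two table formats.**
- Protocol section 4 collects unsolicited AEs only to 28 days after the last dose, and Appendix A limits Visits 8 and 9 to SAE review. Table 91's 6-month row, headed as all related unsolicited AEs, therefore covers a period in which non-serious events were not collected in any cohort.
- Table 105 defines N as recipients of the specified dose, and the daily solicited tables for Cohort E stop at dose 2. Table 97 is out of line with both.

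**The case against.** The strongest reply is that the exposure is partial and disclosed. D and E were observed for part of the time. Table 10 shows completion of follow-up at Day 209 and Table 11 at Day 223; the deviation tables count missed visits, and SAP 15 states the gap. Results are shown by cohort and no hypothesis is tested. The 9.3 rule also has exceptions: solicited maximum severity uses non-missing data, and unsolicited AEs by vaccination use recipients of that dose. All of this is correct. None of it changes the affected percentages, and the dose-recipient rule still keeps people who were dosed but not followed to the end.

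Several stronger readings are tempting but not supported:
- *The plan prints 0/60 with a 6.0% limit for 6-month SAEs.* Tables 91 and 93 have no confidence limits and no column pooling vaccinees; the all-participant columns include placebo. The SAP's 6.0% belongs to dose-limiting AEs in the planned Cohorts A–F. Protocol 11.4.2 plans exact intervals for AEs in aggregate but a listing for SAEs.
- *Cohort E was seen for only 7 days after its last dose.* This is inferred from vital signs; Day 43 remains possible.
- *Nobody in D or E was followed after the last visit.* Missed visits are documented. Whether there was remote contact is not stated, and SAEs could have been reported without a visit.
- *Cohort D's primary AE window is affected.* It is complete.
- *The long-term objective would be declared met.* The SAP is descriptive and makes no such declaration.

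The leftover Post Dose 3 column does not bias a rate by itself, and Table 91's 6-month row can hold SAEs, since Listing 22 places them among unsolicited events. Both are labelling errors, but they invite misreading.

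**Conclusion.** The point stands in limited form. Followed as written, the plan treats the unobserved part of the 6-month window in Cohorts D and E, and of the 28-day window in Cohort E, as event-free. Solicited events are largely unaffected because Cohort E had its 7-day visit after dose 2.

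At 15 per cohort, 40% of participants lack the 6-month visit. The factor of 0.60 requires equal cohort sizes and no recorded events in D and E; the limits in the table are illustrative because the documents give no event counts. For D or E alone, a zero at 6 months over the full cohort N would rest on no scheduled 6-month visit and should be read as incomplete follow-up. The scheduled visits support a 6-month safety conclusion only for Cohorts A–C.

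**What to change.** - **SAP 9.3 and Tables 91–96.** For the 28-day and 6-month windows, show the number whose follow-up reached the end of the window and the number not assessed. Add events per person-time on the Safety Population. Do not use completers plus anyone with an event as the denominator: it keeps every event but drops partly followed event-free people, so one early SAE in Cohort D would read 1/1 at 6 months.
- **Marking.** Flag the 6-month columns for D and E and the 28-day column for E as incomplete follow-up, and list any events seen there.
- **Conclusion.** Limit the 6-month safety statement to Cohorts A–C unless remote follow-up of D and E is documented; if it is, state its dates and use it.
- **Tables 91 and 92.** Restrict the 6-month row to SAEs.
- **Tables 97–104.** Define N as recipients of the specified dose, as Table 105 does, and drop Post Dose 3 for Cohort E.

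The cost is SAP wording, a few shells and a person-time derivation from last-contact dates. No new data collection is needed. Precision at 6 months will look less favourable.

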### 9.3.2. Unsolicited Adverse Events

The proportion of participants reporting at least one unsolicited adverse event will be summarized by MedDRA system organ class and preferred term and treatment group for each vaccination and over all vaccinations. Denominators for percentages are the number of participants who received the vaccination being summarized.

Unsolicited adverse events by participant will be presented in Listing [22](#).

The following summaries for unsolicited adverse events will be presented by MedDRA system organ class, preferred term, vaccination and treatment group:

- Participant listing of non-serious adverse events of moderate or greater severity ([Table 139](#));

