## 9.7. Vital Signs and Physical Evaluations

The baseline value will be defined as the last value obtained prior to the first vaccination/dose of study product. If a participant has repeated vital sign measurements on the same day, the value from the last evaluation will be used for analysis. Post-baseline, in the case of multiple observations (for example, from supplemental visits), the assessment value that is closest to the scheduled visit window will be used in the analyses. All the recorded data will be listed. If observations have the same distance to the scheduled assessment, the latest one will be used.

Vital sign measurements include systolic blood pressure, diastolic blood pressure, pulse, and oral temperature. Grading scales for vital signs are presented in [Table 9](#). Vital signs were assessed at Day 1, Day 8, Day 15, Day 22, Day 29, Day 36, Day 57, Day 114 and Day 209 for Oral and Sublingual Cohorts and at Day 1, Day 8, Day 22, and Day 29 for Intradermal Cohorts. Vital signs will be tabulated by severity, visit, and treatment group ([Table 160](#), [Table 161](#), [Table 162](#), [Table 163](#), and [Table 164](#); [Listing 25](#)).

Physical Examinations were performed at screening to assess general wellness. The following body systems were assessed: head, eyes, ears, nose, and throat; lymph nodes; skin; pulmonary; cardiovascular; abdominal; neurological; and musculoskeletal systems. At subsequent visits including enrollment a targeted physical examination was conducted if indicated based on review of medical history. Findings will be presented in Listing 26.

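### Cohort E's unsolicited-AE proportion is reported for the 28 days after the last dose over the whole Safety Population, although up to 21 of those days have no documented AE review

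*SAP*

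**What the plan says.** One of the four primary safety endpoints in SAP 3.2.1 is related unsolicited AEs, including laboratory AEs, from the first dose to 28 days after the last. SAP 4.5.1 places the end of that window at Day 57 for the oral and sublingual cohorts and Day 71 for the intradermal cohorts.

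For incidence per participant, SAP 9.3 says "the denominator will be the total population size". SAP 6.3.1 defines the Safety Population as "all eligible participants who received at least one dose of study product", and the note under Table 93 describes N as the "number of subjects in the Safety Population (number of subjects at risk". SAP 9.3.2 asks for unsolicited AEs by "treatment group for each vaccination and over all vaccinations" and adds: "Denominators for percentages are the number of participants who received the vaccination being summarized". SAP 6.5 allows no imputation.

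Table 91 (oral and sublingual) has the row "At least one related unsolicited adverse event, through 28 days after the last dose". Table 92 repeats the format for Cohort E, its placebo group, all intradermal participants, and All Subjects.

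On conduct, SAP 4.4.5 gives Cohort E's doses as Days 1 and 22 only. SAP 15 reports that "Cohort D participant Visits 8 and 9 and Cohort E participant Visits 6 through 9 were not conducted". SAP 9.7 places intradermal vital signs "at Day 1, Day 8, Day 22, and Day 29 for Intradermal Cohorts", and the vital-sign shells (Table 160 onward) have no Cohort E line at the third-dose visit. The status of Visit 5 (Day 43) is not stated.

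**The concern.** The row promises 28 days of observation after the last dose. Cohorts A to D have a visit at that point: Visit 7 is Day 57, and the missed Cohort D visits are 8 and 9. Cohort E has no documented contact near it. With a whole-population denominator and no imputation, a participant who was not seen is counted as a participant without an event.

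At stake is a primary safety percentage for the only intradermal cohort dosed, and a pooled percentage that mixes complete and shortened windows under one label. The denominator in SAP 9.3.2 does not repair this. It takes Cohort E out of any third-dose column, but does nothing about lost follow-up after dose 2.

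It looks like an oversight. Other outputs were adapted to the shutdown: Cohort E's daily solicited tables (Tables 131 to 134) stop at dose 2, the vital-sign shells drop the cohort after its last visit, and the solicited maximum-severity percentages use participants with data. The unsolicited-AE rows were left as they were.

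**Working it through.** **Window ends.** The SAP 4.5.1 figures are the day of the third dose plus 28: 29 + 28 = 57 and 43 + 28 = 71. Both reproduce. Cohort E had no third dose, so 28 days after its last dose is 22 + 28 = Day 50.

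**Days without documented review.**
- Follow-up ending Day 29: 50 − 29 = 21 of 28 days (20 to 22 with the ±1 day window of Visit 4).
- If Visit 5 was held on Day 43: 50 − 43 = 7 of 28 days.
- For 12 vaccinees (target number): 12 × 28 = 336 person-days observed by Day 29, against 12 × 49 = 588 to Day 50, or 57%.

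**Size under a constant hazard.** The documents give no AE rate, so this is an assumption shown over a range. Let p be the 56-day risk (Day 1 to Day 57) of an oral or sublingual cohort, with the same hazard in Cohort E. The risk after d days is 1 − (1 − p)^(d/56).

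| p | By Day 29 (d = 28) | By Day 43 (d = 42) | By Day 50 (d = 49) | Day 29 / Day 50 | Day 43 / Day 50 |
|---|---|---|---|---|---|
| 2% | 1.0% | 1.5% | 1.8% | 0.57 | 0.86 |
| 20% | 10.6% | 15.4% | 17.7% | 0.60 | 0.87 |
| 50% | 29.3% | 40.5% | 45.5% | 0.64 | 0.89 |
| 90% | 68.4% | 82.2% | 86.7% | 0.79 | 0.95 |

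The last two columns isolate truncation, because they compare Cohort E with its own complete two-dose window.

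**Comparison with oral and sublingual.** Dividing by p gives 0.50 to 0.76 for follow-up to Day 29 and 0.75 to 0.91 for follow-up to Day 43. Even complete follow-up to Day 50 gives 0.88 to 0.96, because two doses give a 49-day window against 56. At p = 20%, the gap from 20% to 10.6% is 9.4 points: 2.3 from the shorter schedule (20 − 17.7) and 7.1 from truncation (17.7 − 10.6).

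**Size if events cluster.** Suppose all related events fall within 7 days of a dose, with risk q per dose. Nothing after a given dose is then missed. The ratio of two doses to three is [1 − (1 − q)²] / [1 − (1 − q)³]. It is 4.0/5.9 = 0.67 at q = 2% and 51.0/65.7 = 0.78 at q = 30%. All of that gap is the third dose not given.

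**Pooled column.** At target enrolment Cohort E is 15 of 75. With p = 20% and an equal hazard in everyone, the pooled rate is (60 × 0.20 + 15 × 0.106)/75 = 18.1%. With Cohort E complete to Day 50 it is (60 × 0.20 + 15 × 0.177)/75 = 19.5%.

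**Laboratory part.** SAP 9.6 schedules safety laboratory tests after dosing only at the visits that are Days 50 and 71 for the intradermal route. Neither was held, so Cohort E has no scheduled laboratory result after dosing, although Table 142 keeps a maximum post-baseline severity line for it.

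**The case against.** Several objections have force.

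- **Day 29 is not a stated AE cut-off.** It comes from the vital-sign section. Visit 5 is not listed among the missed visits, and Protocol 5.3.4 and 7.6 allow telephone assessment at early withdrawal and unscheduled visits. A reader might infer that nobody followed Cohort E beyond Day 29. The documents do not show that, so 21 days is a ceiling.
- **A constant hazard may not suit the endpoint.** The events are vaccine-related and may well follow doses closely, in which case truncation costs little. This stands, and it is why the size is given as a range.
- **A reader might infer that intradermal dosing will look about half as risky as the other routes.** The documents do not support that as a finding. A ratio near 0.50 needs a constant hazard, a low event rate and follow-up ending on Day 29, and part of it comes from the third dose not given.
- **No comparison of routes is tested.** SAP 6.8 plans no hypothesis test. Cohort E is in Table 92 rather than beside Cohorts A to D in Table 91, and Tables 93 and 94 have no 28-day row. Only All Subjects mixes windows. This limits the harm but does not correct the label.
- **The shutdown is disclosed.** SAP 4.1, 4.4.5, 15 and the notes to Table 1 all report it, and Listing 22 gives days after dose. None of them tells the reader of Table 92 that its 28-day row was not observed for 28 days.

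**Conclusion.** The point holds as a mismatch between label and denominator in a primary safety table. The direction is certain: unobserved days can remove events from the numerator but cannot add any. The size is uncertain. Under a constant hazard, Cohort E would show 0.57 to 0.79 of its own full-window risk if review ended on Day 29, and 0.86 to 0.95 if it ended on Day 43. It would show close to all of it if related events cluster within 7 days of dosing. The ratio to the oral and sublingual cohorts could lie anywhere from about 0.50 to 0.9, and should not be read as an effect of the denominator alone. The pooled effect is smaller, 19.5% to 18.1% in the example. The counts of 12, 15 and 75 are targets, since the SAP does not give actual enrolment. This should be corrected before the tables are produced. It does not undermine the safety data themselves.

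**What to change.** 1. In SAP 9.3 and 15, state Cohort E's actual AE cut-off and whether Visit 5 was held. Label its Table 92 row as running through the last AE review, with that day.
2. Report the rate to 28 days after the last dose for Cohorts A to D only, and leave Cohort E out of the pooled 28-day rate. Keep every Cohort E event in the listings and in its own row.
3. For display across cohorts, add a row matched by dose that every cohort was followed for, such as onset within 7 days after dose 1 or dose 2, with observed person-days. That covers Days 1 to 8 and 15 to 22 for oral and sublingual, and Days 1 to 8 and 22 to 29 for intradermal. A common calendar cut at Day 29 would not match: it leaves 29 − 15 = 14 days after dose 2 in one case and 29 − 22 = 7 in the other.
4. Reconcile the Day 71 window end in SAP 4.5.1 with the doses actually given.

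The cost is SAP wording and a few extra rows from data already held. The price is that no 28-day intradermal rate is claimed.
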